- Provide the participant with the opportunity to ask questions
- Answer any questions that the participant may have
- Set-up the participant, on the computer for their use.

The questionnaire will include the Short Form (36) Health Survey (SF-36) assessment and an assessment of their breathlessness (dyspnoea) by the Modified Borg Dyspnoea Scale (MBS). At visits 2 and 3, it will include questions about symptoms, tests and vaccinations since the previous.

SF-36

The original SF-36 stemmed from the Medical Outcome Study, and it is a 36-item, patient-reported survey of patient health. The SF-36 is a measure of health status. is commonly used in health economics as a variable in the quality-adjusted life year calculation to determine the cost-effectiveness of a health treatment.

Modified Borg Scale (MBS)

The MBS is a 0 to 10 rated numerical score used to measure dyspnoea (breathlessness) as reported by the patient during submaximal exercise and often administered to patients before and after the sixminute walk testing (6MWT). Participants will be asked to grade the severity of their dyspnoea at rest and during activity.

	evised Borg Scale for rading Severity of Dyspnea
0	- Nothing at all
1	- Just noticable
2	- Very slight
3	- Slight
4	- Slight-moderate
5	- Moderate
6	- Some difficulty
	- Moderately severe
	- Sever
9	- Very sever
	- Panic level, maximal shortness of breath

COVID-19 Symptoms, tests and vaccinations

A short series of questions will be asked about any symptoms experienced since the last visit, these questions are repeats of questions asked to ALSPAC participants on 3 previous occasions during the pandemic and will enable us to track convalescence.

A series of questions will be asked about likely exposure to COVID-19 in the 28 days prior to the clinic visit, this provides details required for completion of a risk assessment for the processing of the biological samples.

Participants will be asked if they have been vaccinated, when they received the vaccination and which vaccination they had. This will be vital in understanding results of analysis of the biological samples.

Use of existing ALSPAC samples in this study

ALSPAC has collected peripheral blood lymphocytes, blood, urine and saliva samples at previous research clinics (http://www.bristol.ac.uk/alspac/researchers/our-data/biological-resources/) The participants were asked to consent to "future use" when the samples were taken. Where appropriate consent was obtained for existing samples from the participants in this study cells and serum components may be used to establish a baseline immune phenotype or response pre-exposure to SARS-CoV-2 infection that is matched to individuals within the cohort. These cells and serum components will undergo the same analysis as research samples taken during this protocol.

PARTICIPANT FEEDBACK AND INCIDENTAL FINDINGS

The investigations performed in this study will not lead to incidental findings likely to impact on participants such that feedback to them or their healthcare providers is required. Furthermore, following processing of biological samples obtained, the laboratory analysis is likely to be undertaken at a time period after the specimens are obtained; hence, any results are not in real time for participants in this study Therefore, feedback to participants will not be provided.

In the event of any unexpected disclosure by study participants to the Fieldworker concerning their health status (for example struggling with activities of daily living or reduced exercise tolerance due to breathlessness), participants will be advised to consult their usual healthcare practitioner (e.g. General Practitioner) for further advice and ongoing treatment.

PROCESSING, TRANSPORT, ANALYSIS AND STORAGE OF BIOLOGICAL SAMPLES

Blood, urine and saliva samples will be taken from all consenting participants. Samples will be processed, and aliquots of samples stored for analysis. Samples will be labelled with barcoded ID numbers and personal information will not be passed to researchers analysing the samples. Samples will be stored for future use provided appropriate consent has been obtained. All samples will be used, stored and disposed of in accordance with the Human Tissue Act 2004. [name] is licensed by the Human Tissue Authority for long term storage of samples.

- A laboratory technician will check the REDCap system which will indicate if samples have been taken. The potential blood samples that could be taken are 4 x EDTA tube and 1 x serum tube
- If samples have been taken the technician will collect from clinic. All tubes will be collected at room temperature. If REDCap does not show that samples have been taken within ½ an hour of the participant's appointment time the technician will contact the clinic team.
- On receipt of samples the technician will check that the barcode labels of the samples match the clinic ID on the REDCap system and that all samples taken in clinic match the samples received.
- Consent to individual analyses and storage for future genetic and non-genetic research will be checked. Samples will then be processed according to the consent given. If any consent data is missing the technician will contact the clinic team.
- PBMCs and/or PBLs will be isolated from blood taken in the 3 EDTA tubes which have been kept at room temperature using standard density gradient separation techniques. The sample processing procedure will commence within 3 hours of drawing blood. PBMCs and/or PBLs will be stored in liquid nitrogen and plasma will be stored at -80 °C.
- The 4th EDTA tube will be centrifuged and plasma aliquoted in 200ul and 500ul aliquots for storage at -80 °C. This is the ALSPAC standard protocol and will allow samples to be

comparable to those taken in other ALSPAC clinics. Provided consent was obtained for future genetic analysis then the buffy coat will be stored -80 °C for future DNA extraction. The serum tube will be allowed to clot for 30 mins before centrifugation at 4 °C. Serum will then be aliquoted in 200ul and 500ul aliquots for storage at -80 °C.

- Samples may be sent to other labs both internal and external to the University of Bristol to undertake analyses. The Bristol Bioresource Laboratories will be responsible for the transport of samples from [name] to other labs. For samples to be sent externally they will be shipped on dry ice with next day delivery to maintain sample integrity. A University of Bristol approved courier will be used that has a tracking system so that samples are traceable throughout delivery. The receiving laboratory will acknowledge receipt of samples upon delivery. A list of all samples to be analysed will be sent to the chief technician of the receiving lab, any discrepancies will be reported to either the BBL Chief Laboratory technician or Head of Biosamples. Any specific storage conditions will be adhered to by the receiving lab.
- PBMC/plasma or serum samples will be transferred to the School of Cellular and Molecular Medicine, Biomedical Sciences building, Immunology wing (F Floor) to Prof [name] and Dr [name]'s laboratories (F60-F65). Samples will be stored and used as approved by the UoB Biological Safety Commitee (BGMSC activity #924; CBA1.18.20.1). PBMC samples will be stored in padlocked liquid nitrogen tanks (B floor, liquid nitrogen tank storage room), while plasma/serum samples will be stored in padlocked - 80°C freezers (Prof [name]/Dr [name]'s lab F65; Prof [name]'s lab, B floor). The freezers/liquid nitrogen tanks are all located in access restricted areas accessible to authorized personnel only.
- Any remaining material following analysis will be returned to Bristol Bioresource Laboratories and stored in the ALSPAC biobank, this includes stocks of DNA and RNA.

LABORATORY ANALYSIS

Detection of SARS-CoV-2:

Saliva will be tested for SARS-CoV-2 using the reverse transcriptase polymerase chain reaction (RT-PCR) assay recommended by the World Health Organisation or adaptations thereof as the technique is refined and in conformity with Public Health England standard operating procedures. Briefly, after a viral inactivation step, RNA will be extracted from samples either manually or using an automated platform, reverse transcribed into cDNA, and stored at -70°C. Samples will be prepared and real time PCR for SARS-CoV-2 will be performed using Thermo-Fisher QIAgility and QuantStudio or similar platforms. Viral detection will be expressed quantitively as cycle threshold (Ct) number for samples amplifying below the cut off for each assay.

SARS-CoV-2 specific serum and salivary antibodies:

ELISAs and Western Blots will be used to quantify titres of each antibody isotype (e.g. IgM, IgA, IgG) specific to SARS-CoV-2 viral proteins/epitopes being produced including (but not limited to) the spike glycoprotein, the receptor binding domain (RBD) and nucleoprotein. Techniques such as UREA based ELISA or surface plasmon resonance (SPR), will be used to determine the extent of antibody affinity maturation by calculating the avidity index of antibodies towards the spike glycoprotein and RBD over time (Mann et al. 2014). The neutralising activity of antibodies will be measured using techniques such as a high-throughput pseudovirus neutralization assay using SARS-CoV-2 spike protein pseudotyped lentiviral particles or SARS-CoV-2 microneutralisation assays with live virus.

Analysis of the B-cell response:

To describe the dynamics of the B-cell response we will enumerate and characterise antibody secreting cells (ASCs/plasma cells/plasmablasts), activated B-cells (ABCs) and memory B-cells

(MBCs) at various timepoints. This will be achieved using a combination of techniques which will include (although are not limited to) flow cytometry (via fluorescently labelled viral antigens and markers for ASCs, ABCs versus MBCs, etc.), B-cell ELISpots (Ellebedy et al. 2016; Clutterbuck et al. 2012) and antigen specific B-cell proliferation assays. The heterogeneity and degree of somatic hypermutation (SHM%) in SARS-CoV-2 specific B-cell responses will be determined by B-cell repertoire sequencing using RNA from PBMC and will identify 'public' versus 'convergent' B cells.

In-depth analysis of T-cell responses:

The SARS-CoV-2 specific T-cell response will be assessed in detail at various time points using a range of techniques These will include (but not be limited to) multi-parameter flow cytometry and activation assays such as ELIspots, ELISAs, proliferation assays and Intracellular Cytokine Staining (ICS) after stimulation with antigenic viral proteins and/or their peptide derivatives. In conjunction with these activation assays we will also perform in-depth phenotypic analysis of the antigen-specific T-cell response using multi-parameter flow cytometry. In addition, T-cells will be enumerated and directly characterized ex vivo from human blood using peptide-HLA (p-HLA) tetramers. Prior to some of these experiments we will need to determine the T-cell epitopes that can be recognized by the SARS-CoV-2 specific T-cell response. This will be achieved using a range of techniques such as MHCI binding algorithms, the analysis of previously identified SARS epitopes that are shared with SARS-CoV-2, overlapping peptide libraries and/or immunoproteomics. These candidate epitopes will be validated using patient samples and used to generate p-HLA tetramer reagents, and to perform in-depth phenotypic and functional analysis in conjunction with flow cytometry and T-cell activation assays. As such, for some experiments, it will be necessary to determine the HLA type of the patient or normal donor. In some instances, we may establish T-cell lines and/or T-cell clones that will be used to conduct in-depth analysis as described above, as well as combinatorial peptide library (CPL) analysis to assess T-cell cross-reactivity.

Immuno-phenotyping/Immune profiling (using serum/plasma and/or blood cells):

In-depth immune profiling will be performed at various time points. Flow cytometry will be used to characterise a range of immune subsets in collected samples from controls and different patient groups including those that display features of acute/chronic inflammation or immune activation. These will include: CD4 T cell subsets, CD8 and gamma-delta-T-cells, B-cells, NK and NKT-cells, monocytes, peripheral blood macrophages, as well as myeloid and plasmacytoid dendritic cells, neutrophils and platelets. Pro-inflammatory cytokines/chemokines and other soluble factors associated with the immune response will also be measured in the serum/plasma of the same patients.

Additional Assays

In addition to the assays described above we will be performing additional assays to assess the immune response to COVID-19. This may include techniques such as B-cell receptor (BCR) sequencing, T-cell receptor (TCR) sequencing, NanoString analysis, RNAseq, single cell analysis, transciptomics, proteomics, cell signalling analysis, analysis of cellular cytotoxicity for e.g. using XCELLigence RTCA systems etc. We will also apply the techniques described above to examine cross-reactive immune responses against other pathogens such as the circulating human CoVs, so that we can quantify T-cell, B-cell and antibody cross-reactivity and define how cross-reactivity may influence response to infection and/or vaccination. T-cell epitopes identified as described above will also be used to generate T-cell lines or clones that can be used for in-depth phenotypic and functional analysis (such as cross-reactivity against other viruses, TCR sequencing etc..) and generate T-cells with potential therapeutic benefit. SARS-CoV-2 specific T-cells will be assessed for reactivity against target cells such as SARS-CoV-2 infected cells to confirm whether they are SARS-CoV-2 specific.

Descriptive analysis of other measures

We will describe the cases (and controls) according to a number of pre-pandemic measures including gender, BMI, lung function, occupation and other sociodemographic measures. Changes over time

Protocol v2.0 02/02/2021

during the convalescent period will then be examined. This will focus on changes in self-reported measures of SF36 and dyspnoea and the objective respiratory function tests. Depending on the number of controls enrolled, we may be sufficiently powered to compare cases with controls in terms of the key outcomes.

DATA MANAGEMENT

Data will be collected on a computer-based system which is already in place and uses the REDCap software (http://www.project-redcap.org/). Any relevant research data will be extracted, cleaned and prepared for future use. All electronic data and human tissue are stored securely on University of Bristol premises.

Confidentiality:

Only anonymised data are shared with researchers. Strict procedures for collaboration are in place, which prevent collaborators linking data without our knowledge. Addresses, postcodes, e-mail addresses and telephone numbers are stored securely on separate servers to those which store the scientific data. Researchers with access to data files are denied access to the administration databases and vice versa. Descriptive analyses will be performed in-house

ADVERSE EVENT REPORTING

Risk assessments are carried out on all clinic measures and described in our risk management plan, and risks minimised via implementation of an action plan. Any adverse events will be recorded using University of Bristol incident reporting system – all incidents are thoroughly investigated, and root-cause analysis conducted.

Rigorous Health & Safety systems are in place with a series of SOPs available to deal with identified risks e.g. needle stick injuries.

COMPENSATION FOR PARTICIPANTS

Study participants will receive £10 as a thank you for each visit completed. This is based on what participants have previously received for taking part in similar activities within ALSPAC.

QUALITY CONTROL AND QUALITY ASSURANCE

The Fieldworker will be fully trained in the procedures ensuring specialist training where appropriate. Data collected on each participant will be recorded by a fully trained Fieldworker at the time of collection. The data collection system is computer based and has many data checks built into the system, including range checks and prompts for missing fields, thus minimising data entry errors. The investigators will be responsible for data quality

INSURANCE

The study is insured by the University of Bristol.

SPONSORSHIP AND ETHICAL ARRANGEMENTS

The University of Bristol is the research sponsor for this study.

This study will be reviewed by an NHS research ethics committee. Any amendments will be submitted for review to the sponsor and ethics committee prior to implementation.

The application has also been reviewed by the ALSPAC Executive, anonymous reviewers and grant board members for the European Research Council, the ALSPAC independent Law & Ethics Committee and the Children of the 90s original cohort advisory panel (OCAP).

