In acute SARS-CoV-2 infection, lymphopenia may occur with drastically reduced numbers of CD4 and CD8 T-cells, with some evidence that the degree of lymphopenia correlates with COVID-19 disease severity and mortality. Currently, little is known about specific phenotypic and/or functional T-cell changes associated with COVID-19 and whether boosting or limiting T cell activation would represent candidate therapeutic options to target hyperinflammation.

To facilitate an in-depth analysis of the phenotypic and functional properties of SARS-CoV-2specific T-cells it is important to identify the SARS-CoV-2 epitopes/antigens that are targeted by effector and memory T-cells, as well as their immunodominance across a number of patients that express different chosen HLA molecules. While initial bioinformatic and experimental work has given some evidence of the major protein targets of the T-cell response, the identity of the immunodominant T-cell epitopes remains to be defined. This knowledge is critical for the design of vaccines that aim to elicit responses in both B and T-cell arms of the adaptive immune system as well as for the evaluation of SARS-CoV-2 specific T-cell immunity after vaccination and during natural infection.

This protocol therefore proposes a structured sampling framework over 9 months with participants recruited at different time points following SARS-CoV-2 infection. At each visit, peripheral blood mononuclear cells will be extracted from participants. The immune profile of T-cells will be analysed to determine the nature and duration of T-cell immune responses following SARS-CoV-2 infection. By defining this response, and the protein targets of the T-cell response, this study will directly contribute to the understanding of the immune response against SARS-CoV-2. The results from this study can be directly compared to T-cell responses in individuals who receive any future COVID-19 vaccination, and thus this study will act to provide a comparator for the efficacy of immunological responses in vaccinated individuals.

B-cell Mediated Immunity

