Humoral immune responses to coronaviruses are a particularly important area of study as neutralising antibody is believed to be the principle mode of immune-mediated protection to reinfection, as well as a likely mode of clearance in primary infection. Recently published peer reviewed articles and non-peer reviewed preprints indicate that most individuals infected with SARS-CoV-2 (as determined by RT-PCR) develop detectable antibody responses between 10- and 20-days post symptom onset. There have been mixed findings regarding the severity of symptoms and the level of antibody responses, with some studies showing no relationship between case severity and levels of antibody.

It is important to consider a potential role for pre-existing cross-reactive antibodies due to prior infection with other common human CoVs (which cause the common cold) on the outcome to SARS-CoV-2 infection. Studies exploring the role of cross-reactive antibodies to other CoVs suggest that there is some degree of protection provided by antibodies raised against heterogenous CoVs within the same family (i.e. alpha or betacoronviridae).

Importantly, the longevity of antibody responses and the level of neutralising antibody, is not known. Deciphering the range relationship between the severity of infection and longevity of protective humoral immune responses is crucial for predicting future outbreaks and the future relationship we will have with SARS-CoV-2; many studies assuming a short lived antibody responses (as is the case with other common CoVs) point towards SARS-CoV-2 becoming a seasonal respiratory virus.

Currently the duration, type and efficacy of antibody response to SARS-CoV-2 remain unclear. There is thus a pressing need to define the antibody response, as this will provide a critical insight into the immune response to SARS-CoV-2, enabling the assessment of potential vaccines and implementation of public health interventions. Understanding the duration of the antibody response to SARS-CoV-2 will enable more accurate modelling of infection in predicting future outbreaks and the likely future dynamics of SARS-CoV-2 infection

Rationale

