Information from these along with linked NHS medical records data will be used to identify potential participants. Based on seroprevalence estimates, ALSPAC cohort size, and estimations of typical response to similar studies, this study therefore estimates recruiting approximately:

- 100 cases of previous SARS-CoV-2 infection at Visit 1 (approx. upper limit of 250 cases)
- 100 control individuals without previous SARS-CoV-2 infection age, sex and symptom matched to cases and 100 random controls without previous SARS-CoV-2 infection (approx. upper limit of 250 controls)

Where needed (i.e. if there are large numbers of potential cases), priority will be given to participants with pre-pandemic measures of BMI and lung function (objectively assessed at the age of 24 years) and previous biological samples.

[figure not shown]
As part of an initial visit, blood will be taken and the antibody and T-cell response to SARS-CoV-2 determined. Individuals who are cases with a SARS-CoV-2 antibody response and/or a positivie T-cell response will be enrolled in the SARS-CoV-2 arm. Individuals who are cases with information available that there is no detectable SARS-CoV-2 antibody or T-Cell response will be considered seronegative and will not be required to participate further in the study. Individuals who are recruited as controls and have a confirmed SARS-CoV-2 antibody negative response will be enrolled into the control arm for two remaining visits, sufficient negative controls will be recruited to allow for the possibility that some controls will become infected with SARS-CoV-2 during the duration of the study and will not be eligible to complete all four visits. Those who were initially recruited as controls

who have subsequently tested positive will also be retained in the study and will move from control arm to case arm as appropriate. Where cases are no longer available, but new cases are defined, sample size will be maintained by the recruitment of new case events.

Pilot study

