- (9) Assess prevalence of cross-reactivity against circulating CoVs and how this might influence the outcome of response to COVID infection.
- (10) Assess changes in the exercise capacity test, SF36 and self-reported dyspnoea during the convalescent period.

Study design

This is a longitudinal observational cohort study of adults within the Bristol area, conducted on individuals who may fall into the following groups of patients:

- (1) healthy seronegative controls (some of whom may become infected during the study),
- (2) asymptomatic/pauci-symptomatic
- (3) symptomatic infection not requiring hospitalisation,
- (4) moderate illness not requiring hospitalisation,
- (5) hospitalised patients who did or did not require mechanical ventilation

Sampling framework

Current estimates of COVID-19 prevalence in the SW England (based on seroprevalence data) range between 2-6%, with age and time since infection contributing to differences in patient groups. It is therefore reasonable to assume that seroprevalence is approximately 3%. ALSPAC have undertaken 5000 serological SARS-CoV-2 tests on cohort participants; therefore, if only 3500 of these are returned, we would expect to identify 100 individuals seropositive to SARS-CoV-2. If only 50% of these 100 individuals wish to enter into this study, the cohort of seropositive individuals would be 50.

The number of seropositive individuals will be increased by incorporating ALSPAC cohort individuals who:

- 1. self-report as being highly likely to have had COVID-19 infection (from either positive SARS-CoV-2 PCR test performed at NHS care facility, COVID-19 testing site or home testing), **OR**
- 2. have been told by a physician that, in the opinion of that doctor, they have had a clinical illness likely to be COVID-19 **OR**
- 3. based on a combination of symptoms they are likely to have been cases

DATA COLLECTION

Cases - inclusion criteria

This study will be undertaken on participants of the ALSPAC cohort meeting the following criteria:

- 1. Aged 25 or over, AND
- 2. Individuals who have undergone SARS-CoV-2 antibody testing through the ALSPAC SARS-CoV-2 serology study (IRAS 289493), **OR**
- 3. Individuals who self-report or through linkage to official health records as being highly likely to have had COVID-19 infection (from either positive SARS-CoV-2 PCR test performed at NHS care facility, COVID-19 testing site or home testing), **OR**

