- 4. Individuals who have been told by a physician that, in the opinion of that doctor, they have had a clinical illness likely to be COVID-19.

Control participants – inclusion criteria

- 1. Aged 25 or over, AND
- 2. Individuals who self-report as not experiencing symptoms of COVID-19 via the symptom survey and do not have case status through linkage to official health records, **AND**
- 3. Self-report as not having had positive SARS-CoV-2 molecular test, AND
- 4. Are confirmed SARS-CoV-2 seronegative at Visit 1 and then at visit 2

Exclusion criteria for both controls and cases

- 1. Do not wish to participate in this research study
- 2. Participants taking blood thinners (e.g. warfarin) or with a known clotting disorder
- 3. Do not meet eligibility criteria for respective arm

Invite procedure

An initial invitation email (*Initial invite v2*), and link to a participant information sheet (*Information Sheet v2*) will be sent to eligible participants, via contact details held, with participant consent, in the ALSPAC contact management system. Appointments will be offered on a range of days and times, including weekends. Participants will be able to respond by telephone or email. A reminder email will be sent if there is no response after one weeks (*Reminder email v2*) and if they do not respond after a further week they will be called by a member of the ALSPAC research team. This is an invitation procedure used previously within ALSPAC and study participants are familiar with contacts from the study by these methods.

Following the initial visit, samples will be analysed for current serological response. Those cases who are seropositive or T-Cell positive at Visit 1 and all controls whether confirmed as seronegative or seropositive will be invited (*follow up invite v2*) to complete repeat visits 4 months, and 8-12 months post visit 1. Those not eligible to continue the study will be notified by email (*follow up no visits v2*).

Where cases are no longer available, but new cases are defined, sample size will be maintained by the recruitment of new case events.

Before the clinic visit - (Visits 1-4)

Once booked for an appointment, the participant will be sent a confirmation email (*Confirmation letter v1, with a link to visiting children of the 90s COVID-19 information sheet*) and then an appointment reminder call the day prior to their appointment this will include a check for any current COVID-19 symptoms.

At the clinic visit

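### A recently infected case can be dropped as seronegative on a single early Visit 1 sample, because the protocol sets neither a minimum interval nor a re-test

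*Protocol*

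**What the plan says.** - **Time to detectable antibody.** The protocol's background section Antibody Responses states that most PCR-confirmed individuals "develop detectable antibody responses between 10- and 20-days post symptom onset".
- **Timing of entry.** The background section on T-cell immunity plans a sampling framework "with participants recruited at different time points following SARS-CoV-2 infection". It gives no lower limit.
- **Case entry.** Cases - inclusion criteria admits people tested in the ALSPAC serology study. It also admits "Individuals who self-report or through linkage to official health records as being highly likely to have had COVID-19 infection" and people told by a physician that "in the opinion of that doctor, they have had a clinical illness likely to be COVID-19". None of these routes carries a date or interval condition.
- **Replacement.** Participant Selection and Invite procedure both say: "Where cases are no longer available, but new cases are defined, sample size will be maintained by the recruitment of new case events".
- **Retention.** Under Participant Selection, "Individuals who are cases with a SARS-CoV-2 antibody response and/or a positivie T-cell response will be enrolled in the SARS-CoV-2 arm". Cases for whom "there is no detectable SARS-CoV-2 antibody or T-Cell response will be considered seronegative" leave the study. No repeat sample is mentioned.
- **Follow-up clock.** Invite procedure times the repeat visits at 4 months and at 8 to 12 months after Visit 1, not after onset.
- **Timing rules at the visit.** Infection Control Measures postpones the visit of anyone with symptoms and applies a 14-day household quarantine. The questionnaire asks about exposure in the preceding 28 days, but for the risk assessment of sample handling and not for eligibility.

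**The concern.** The drop rule treats one Visit 1 sample as enough to show that a case has no response. By the protocol's own figure this is not so for a sample taken within about 20 days of onset: a person who will respond may not yet have measurable antibody. If T cells are also negative at that moment, the person is labelled seronegative and follow-up stops.

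The primary objective is the magnitude and duration of memory, and the Rationale asks in what proportion of patients memory occurs. Dropping early-sampled responders adds false non-responders to that proportion. It also removes their later visits for good. A statistical analysis plan can handle timing among people who stay, but it cannot restore visits that never took place. The eligibility and re-test rules belong in the protocol, so this gap is not one that a plan would normally fill.

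**Working it through.** **1. Is there a minimum interval anywhere?** Participant Selection, Sampling framework, the case criteria, Invite procedure, Infection Control Measures and the questionnaire section were checked. None sets one. Postponement while symptomatic fixes no number of days and does nothing for people without symptoms or with quick recovery. The invitation steps (email, reminder after one week, call after a further week) may lengthen the interval, but a prompt reply is not delayed by them.

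**2. Who is exposed?** Cases already seropositive in the ALSPAC survey are past seroconversion. The risk lies with entry by PCR, self-report, linkage or physician opinion, and with replacement cases. Of these, only people negative on both antibody and T cells leave.

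**3. How likely is an early sample to be antibody-negative?** The protocol gives a range of 10 to 20 days and no distribution, so a shape must be assumed.
- Uniform: P(negative at day t) = (20 − t)/10 for t from 10 to 20.
- Normal, mean 15 days, with 95% or 80% of people inside 10 to 20 days: SD = 5/1.96 = 2.55 or 5/1.28 = 3.90.

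| Day after onset | Uniform | Normal, 95% inside | Normal, 80% inside |
|---|---|---|---|
| 12 | 80% | 88% | 78% |
| 14 | 60% | 65% | 60% |
| 18 | 20% | 12% | 22% |
| 20 | 0% | 2.5% | 10% |
| 21 | 0% | 0.9% | 6.2% |

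Beyond the protocol's own upper limit, most of the risk has gone.

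**4. How many of about 100 planned cases might be dropped?** Let r be the share of cases seen evenly over days 7 to 21, and q the share of antibody-negative cases already T-cell positive. The protocol gives neither. Under the uniform shape, the mean antibody-negative share over that window is (3 × 1 + 10 × 0.5 + 1 × 0)/14 = 8/14 = 0.571. Dropped per 100 = 100 × r × 0.571 × (1 − q).

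| r | q = 0 | q = 50% | q = 90% |
|---|---|---|---|
| 0% | 0 | 0 | 0 |
| 5% | 2.9 | 1.4 | 0.3 |
| 10% | 5.7 | 2.9 | 0.6 |
| 20% | 11.4 | 5.7 | 1.1 |

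**5. Does day 20 also make a safe starting value for persistence?** Take an illustrative curve, none of it from the protocol: a 3 log2 rise from day 10 to a peak at day 30, then a 90-day half-life. Relative to peak, the level is −3(30 − t)/20 before day 30 and −(t − 30)/90 after it. Change over the 122 days to the 4-month visit:
- start at day 30 or later: −122/90 = −1.36 log2;
- start at day 21: −113/90 + 1.35 = +0.09;
- start at day 25: −117/90 + 0.75 = −0.55.

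So a case who met a 20-day rule could still show a misleading first change. The 10-to-20-day figure marks detectability, not peak. This is why the fix relies on time since onset and not on a booking floor alone.

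**The case against.** The best case for the plan is that early attendance should be rare and partly intended. The serology survey is complete, and many cases will come from it or from questionnaires and linkage, well after infection. Replacement is conditional, not continuous. The antibody-or-T-cell rule keeps many early cases. Varied timing is stated design, and the protocol expects innate activation to be short-lived, so early samples serve the innate and B-cell kinetics objectives. A rigid 20-day floor would discard them. All of this stands. It limits the number affected and argues against a hard exclusion. It does not justify ending follow-up on one sample that the protocol's own figure shows may be too early.

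Three stronger readings are tempting and are not supported:
- **That the design hides waning.** A Visit 1 value on the rising limb distorts only a contrast against Visit 1 that ignores time since onset. The protocol specifies no such contrast, an analysis plan could model time since onset, and the change from Visit 2 to Visit 3 would still show the decline.
- **That early-sampled cases contaminate the controls.** Dropped cases leave; they do not change arm. The control criteria also require seronegativity at Visits 1 and 2.
- **That a known share of cases is misclassified.** The protocol gives no distribution of time since infection, so zero is compatible with the text.

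**Conclusion.** The gap is real and narrow. With no minimum interval and no re-test, following the protocol as written can drop a true responder on one early double-negative sample, and that loss cannot be repaired in analysis. The number is not computable from the protocol. Under the assumptions shown it runs from none to about 11 per 100 cases, and to about 1 or fewer if 90% of the antibody-negative cases are already T-cell positive. It is probably small. The conclusion that early samples can mislead rests only on the protocol's 10-to-20-day figure and its drop rule; the sizes rest on the assumed distributions and attendance shares. This is a cheap improvement, not a threat to the study's main conclusions.

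**What to change.** 1. Record at Visit 1 the date of symptom onset, or of the first positive test if there were no symptoms. The protocol places its symptom and test questions at Visits 2 and 3 and lists no onset date at Visit 1, although earlier questionnaires or linkage may supply one.
2. Where practicable, book Visit 1 after the protocol's own 20-day limit has passed.
3. If Visit 1 falls within 20 days, do not apply the drop rule to that sample. Keep the case and re-test antibody and T cells at the already planned 4-month visit before classing the person as seronegative. Read that result alongside the infection and vaccination history since Visit 1, which the questionnaire already collects.
4. Do not use the early value as the start of the persistence series, and analyse persistence by time since onset.
5. Keep the early samples for the innate and B-cell kinetics objectives.

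Cost: one extra date, and a few true non-responders retained for one more visit. No new visit is needed.
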